2. OBJECTIVES

The primary objectives of the study are:

- Determine the treatment effect of rHuPH20 or placebo control injection on the exposure to topical nickel allergen (Treatment Regimens 1 and 2)
- Determine the time to onset and severity of cutaneous reaction to nickel allergen after pre-treatment with rHuPH20 or placebo control (Treatment Regimen 2)
- Assess the safety and tolerability of the rHuPH20 injection

Secondary objectives include:

- Proportion (%) of subjects who, with pre-treatment, have a ≥ 1 grade reduction of the cutaneous reaction to nickel sulfate in at least one patch region at 48 hours
- Proportion (%) of subjects with a ≥ 1 grade reduction of the cutaneous reaction to nickel sulfate in at least one patch region after treatment
- Proportion (%) of subjects that have a ≥ 1 grade reduction of the cutaneous reaction to nickel sulfate in at least one patch region at Days 4, 5, 6, 7 and 14.
- Safety and tolerability of the injection based on AEs, physical examinations, and vital signs

Descriptive-Only parameters include:

- Chromometer readings of the allergen test sites on Day 1, Day 3 (48 hrs), Day 4 (72 hrs) and Day 5 (96 hrs) after the placement of the patches
- TEWL (Trans-epidermal water loss) assessment on Day 1, Day 3 (48 hrs), Day 4 (72 hrs) and Day 5 (96 hrs) after the placement of the patches

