8.1 Primary Variables

The primary efficacy endpoint will be based on the International Contact Dermatitis Research Group (ICDRG) Scoring Scale. Using the ICDRG Scoring Scale, each score will be assigned a Sponsor-defined “grade”. Scores with stronger reactions will be assigned grades with higher values with a maximum grade of 3; scores with weaker reactions will receive lower values with a minimum grade of 0. Grade assignments based on the ICDRG Scoring Scale are shown in the table below.

International Contact Dermatitis Research Group (ICDRG) Scoring Scale

Grade	Score	Interpretation
0	-	Negative reaction
1/2	?	Doubtful reaction; faint macular erythema only
1	+	Weak (nonvesicular) positive reaction; erythema, infiltration, papules, vesicles
2	++	Strong (vesicular) positive reaction; erythema, infiltration, papules, vesicles
3	+++	Extreme positive reaction; bullous reaction
NA	IR	Irritant reaction of different types

Treatment effect of rHuPH20 or placebo control injection on the exposure to topical nickel allergen will be assessed using ICDRG grades for Treatment Regimens 1 and 2 at Day 3 through Day 7 and Day 14.

Regimen 2 only: For each subject, the day of maximal ICDRG score will be determined for each injection type (rHuPH20 and Placebo). The maximal ICDRG score will be the highest score reported for each subject. If the maximal ICDRG score for a particular subject is reported more than one time, the first instance will be used to determine the day when the maximal ICDRG score was reached.

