9.1 Statistical Analyses

The primary analysis is the pair-wise intra-subject comparison of endpoint parameters for the injections with and without rHuPH20. The secondary analysis covers safety and other endpoint parameters (see Section 10).

ICDRG scores will be shown for Treatment Regimen 1 and Treatment Regimen 2 by injection types (rHuPH20 or Placebo) at Baseline, Day 4, Day 5, Day 6, Day 7 and Day 14. ICDRG scores will be reported by subject using figures (Figure 1) and listings (Listing 8).

A qualitative medical review of the ICDRG scores will be used to investigate:

- Possible treatment effect of rHuPH20 or placebo control injection on the exposure to topical nickel allergen.
- Proportion of subjects that have a ≥ 1 grade reduction in at least one patch region.

At the conclusion of the study, findings from the medical review will be summarized in the clinical study report.

For Treatment Regimen 2, the day of maximal ICDRG Score will be used to assess the possible effect each injection type has on the onset of reaction to topical nickel allergen. The day of maximal ICDRG Score will be summarized for each injection type using counts and percentages (Table 6.1/6.2). Possible days of maximal ICDRG Score include

the following: Day 4, Day 5, Day 6, Day 7, and Day 14. If the maximal ICDRG Score for an injection type occurred prior to treatment, the subject will be reported as never having had an ICDRG Score more severe than Day 3 for summary purposes.

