APPENDIX A: LIST OF TABLES, LISTINGS AND FIGURES

List of Tables

Table Number	Table Description
1	Subject Disposition
2	Demographic and Baseline Characteristics
3	Abnormal Medical History
4	Hematology and CBC with Differential at Screening
5	Incidence of Clinically Significant Laboratory Abnormalities at Screening
6	Day of Maximal ICDRG Score
7	Adverse Events by System Organ Class (Safety Population)
8	Adverse Events by System Organ Class and Severity [1] (Safety Population)
9	Adverse Events by System Organ Class and Relationship to Study Drug [1] (Safety Population)
10	Serious Adverse Events by System Organ Class (Safety Population)
11	Adverse Events Leading to Discontinuation of Study Drug or Premature Withdrawal of From Study
12	Adverse Events by System Organ Class and Injection Type (Safety Population)
13	Vital Signs (Safety Population)
14	Physical Examination (Safety Population)
15	Concomitant Medications (Safety Population)

List of Data Listings

Listing Number	Listing Description	CRF Plate(s)
1	Subject Disposition	Derived
2	Inclusion/Exclusion Criteria	2,3,4
3	Demographics	1
4	Medical History	5
5	Hematology and CBC with Differential	8
6	Lab Normal - Hematology	350
7	Pregnancy Test	9
8	ICDRG Score	13,15
9	TEWL (Trans-Epidermal Water Loss) Assessment	17
10	Digital Photographs	17
11	Chromometer	18
12	Subject Diary	19
13	Screening Nickel Sulfate and Vehicle Control Patches	11
14	Study Drug Administration – Treatment Regimen 1	12,13,14
15	Study Drug Administration – Treatment Regimen 2	15,16
16	Adverse Events	97
17	Serious Adverse Events	97
18	Vital Signs	7
19	Physical Examination	6,10
20	Comments	96
21	Prior and Concomitant Medications	98
22	Deaths	101
23	Subject Visit	Derived

List of Figures

Figure Number	Figure Description
1	ICDRG Scores by Day
2	Individual TEWL Scores by Day and Injection Site
3	Individual a-Scale Chromometer Baseline Corrected Scores by Day and Injection Site

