Laboratory Parameter	ITT (N=)	Safety (N=)	Evaluable (N=)
WBC (X 1000/uL)			
N	n	n	n
Mean (SD)	xx.x (xx.xx)	xx.x (xx.xx)	xx.x (xx.xx)
Median	xx.x	xx.x	xx.x
Min, Max	xx, xx	xx, xx	xx, xx
RBC (X Mil/uL)			
N	n	n	n
Mean (SD)	xx.x (xx.xx)	xx.x (xx.xx)	xx.x (xx.xx)
Median	xx.x	xx.x	xx.x
Min, Max	xx, xx	xx, xx	xx, xx
..			

path\t_program.sas date time

Programmer note: Table will include the following hematology parameters: Hemoglobin (g/dL), Hematocrit (%), Platelets (X 1000/uL), Neutrophils (segs) (%), Neutrophils (bands) (%), Lymphocytes (%), Monocytes (%), Eosinophils (%) and Basophils (%).

Table
Incidence of Clinically Significant Laboratory Abnormalities at Screening
All Subjects

Any Clinically Significant Abnormalities?	ITT (N=)	Safety (N=)	Evaluable (N=)
WBC	n (%)	n (%)	n (%)
RBC	n (%)	n (%)	n (%)
Hemoglobin	n (%)	n (%)	n (%)
Hematocrit	n (%)	n (%)	n (%)
Platelets	n (%)	n (%)	n (%)
Neutrophils (segs)	n (%)	n (%)	n (%)
Neutrophils (bands)	n (%)	n (%)	n (%)
Lymphocytes	n (%)	n (%)	n (%)
Monocytes	n (%)	n (%)	n (%)
Eosinophils	n (%)	n (%)	n (%)
Basophils	n (%)	n (%)	n (%)

path\t_program.sas date time

Table 6.1
Day of Maximal ICDRG Score
Evaluable Population

Day of ICDRG Maximal Severity Score	Treatment Regimen 2 (N=)	
	rHuPH20	Placebo
Never had an ICDRG Score More Severe than Day 3	n (%)	n (%)
Day 4	n (%)	n (%)
Day 5	n (%)	n (%)
Day 6	n (%)	n (%)
Day 7	n (%)	n (%)
Day 14	n (%)	n (%)

Note: For both injection types (rHuPH20 and Placebo), each subject will contribute one result based on the single most severe patch assessment reported.
path\t_program.sas date time

Programmer Note: Table 6.2 will contain the same information for the ITT population.

Table
Treatment Emergent Adverse Events by System Organ Class
Safety Population

System Organ Class / Preferred Term	Safety Population (N=)	
	Number of Subjects [1]	Number of Events
Subjects Reporting at Least One Adverse Event	n (%)	n
System Organ Class 1	n (%)	n
Preferred Term 1	n (%)	n
Preferred Term 2	n (%)	n
.		
System Organ Class 2	n (%)	n
Preferred Term 1	n (%)	n
Preferred Term 2	n (%)	n

[1] At each level of summation (overall, system organ class, preferred term), subjects reporting more than one adverse event are counted only once.
path\t_program.sas date time

Table
Treatment Emergent Adverse Events by System Organ Class and Severity
Safety Population

System Organ Class / Preferred Term [1]	Safety Population (N=)				
	Mild	Moderate	Severe	Life Threatening	Fatal

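### Table 6.1/6.2 counts Regimen 2 subjects who never reacted together with those already at their worst on Day 3, shows no grade, and uses day of peak to judge onset

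*SAP*

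**What the plan says.** SAP 2 gives as a primary objective for Regimen 2: "Determine the time to onset and severity of cutaneous reaction to nickel allergen after pre-treatment with rHuPH20 or placebo control". SAP 9.1 supplies the measure: "the day of maximal ICDRG Score will be used to assess the possible effect each injection type has on the onset of reaction". Four rules decide where a subject is counted.

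- SAP 8.1, grading: "scores with weaker reactions will receive lower values with a minimum grade of 0".
- SAP 8.1, repeated maxima: "the first instance will be used to determine the day when the maximal ICDRG score was reached".
- SAP 9.1, maximum reached before treatment: "the subject will be reported as never having had an ICDRG Score more severe than Day 3 for summary purposes". Regimen 2 is first injected on Day 1, so this can only mean before the Day 3 injection. Day 3 is also the first ICDRG reading of these sites.
- Table 6.1 footnote, for each injection type: "each subject will contribute one result based on the single most severe patch assessment reported".

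The shell in SAP Appendix B has six rows: "Never had an ICDRG Score More Severe than Day 3", then Days 4, 5, 6, 7 and 14. It has one column per injection type, no row for absence of reaction, and no grade. In the SAP Appendix A list, "Day of Maximal ICDRG Score" is the only efficacy table. Tables 1 to 5 cover disposition and baseline; Tables 7 to 15 cover safety and concomitant medication.

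Scores themselves are presented by subject, in Figure 1 and Listing 8, and SAP 9.1 leaves treatment effect to a qualitative medical review. No formal comparison is planned. Protocol section 8 nevertheless has dermatitis scoring summarized by treatment group, and SAP 4 has categorical variables summarized by counts and percentages.

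**The concern.** The first hypothesis in SAP 9 is that pre-treatment makes the reaction less severe. Its best outcome is a site that never reacts, and the one efficacy table has no place for that outcome. Subjects are patched at a concentration that gave + or ++ at the 48-hour screening reading (Protocol 5.1.1), so placebo sites can be expected to be positive by Day 3. Placebo subjects who peak at Day 3 would then share a row with rHuPH20 subjects in whom the reaction was fully prevented.

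The table also carries neither half of the objective cleanly. It contains no severity, and its time variable is the day of the peak, not of the first positive reading.

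**Working it through.** The documents state no figure on this point, so there is none to reproduce. The check applies the SAP rules to example courses, counts what the first row can hold, and then illustrates the size.

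**1. Example courses.** Each is the worse of the two sites for one injection type, read on Days 3, 4, 5, 6, 7 and 14.

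| Course | Maximal grade | Row in Table 6.1 |
|---|---|---|
| Negative at every visit | 0 | First row |
| Doubtful at Day 3 only | 1/2 | First row |
| + at Day 3, then fading | 1 | First row |
| ++ at Day 3, then fading | 2 | First row |
| +++ at Day 3 and persisting | 3 | First row |
| Doubtful at Day 4 only | 1/2 | Day 4 |
| + from Day 3, rising to ++ at Day 6 | 2 | Day 6 |
| Negative until + at Day 6 | 1 | Day 6 |

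The SAP does not spell out where the all-negative subject goes. The placement follows from the rules: the maximum is 0, it is first seen at Day 3, and the row label is literally true of that subject. The last two courses share a row, although the first grade of 1 or more is at Day 3 in one and at Day 6 in the other.

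**2. What the first row can hold.** There are five grades and six readings, so 5^6 = 15,625 possible courses. A course falls in the first row when no later reading exceeds Day 3. If the Day 3 grade is the k-th lowest, there are k^5 such courses: 1, 32, 243, 1,024 and 3,125 for grades 0, 1/2, 1, 2 and 3, together 4,425. These count possibilities and are not expected frequencies. They show that the row admits every grade.

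**3. Illustration of size.** Inputs: 20 subjects (the planned evaluable number, SAP 11). Assumptions: every placebo subject reacts; a share p = 50% is negative throughout on rHuPH20; the other rHuPH20 subjects behave like placebo; a share q of reactors peaks after Day 3. The documents give neither p nor q, so q is varied.

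- First row, rHuPH20: 20[p + (1 − p)(1 − q)]
- First row, placebo: 20(1 − q)
- Separate no-reaction row: 20p = 10 for rHuPH20, and 0 for placebo by assumption

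| q | First row, rHuPH20 vs placebo | No-reaction row |
|---|---|---|
| 0% | 20 vs 20 | 10 vs 0 |
| 10% | 19 vs 18 | 10 vs 0 |
| 25% | 17.5 vs 15 | 10 vs 0 |
| 50% | 15 vs 10 | 10 vs 0 |

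The first-row difference is 20pq: 0, 1, 2.5 and 5 subjects, against a true difference of 10. It is also ambiguous. With no prevention at all, 15 vs 10 arises if 25% of rHuPH20 reactors and 50% of placebo reactors peak late: 20(1 − 0.25) = 15 and 20(1 − 0.50) = 10. The same counts then mean an earlier peak on rHuPH20.

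**The case against.** The strongest reply is that Table 6 is not how the plan judges treatment effect. SAP 9.1 gives that task to a medical review of the individual scores. Figure 1 shows all eight sites from Day 3 with treatment labels, and Listing 8 prints every score and marks the maximum for each injection type. This is a descriptive pilot with no decision rule attached to the table. All of this stands, and it limits the point to the aggregate summary.

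A reader might infer three stronger things, none of which the documents support:

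- **That prevention would go unseen under the plan.** It would not; it can be read from Figure 1 and Listing 8.
- **That the two columns must coincide.** They coincide only at q = 0. At larger q the first row does differ, though by less than the true difference and with two possible meanings.
- **That lowering the grade alone must leave every row unchanged.** That depends on the course. A subject at + from Day 3 who would have reached ++ at Day 6, but is held at +, moves from the Day 6 row to the first row.

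The 10 vs 0 contrast also depends on the assumption that every placebo subject reacts.

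The SAP 8.2 reduction endpoint at 48 hours, set against a Day 3 baseline (SAP 8.4), is a separate issue and adds no weight here.

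**Conclusion.** The point holds for the aggregate summary. As written, the only efficacy table listed cannot identify subjects in whom the reaction was fully prevented, shows nothing about severity, and treats day of peak as evidence on onset, for an objective the SAP calls primary. Under the stated assumptions, a true difference of 10 in 20 subjects appears as 0 to 5 in the first row for q between 0 and 50%. The size rests on assumed p and q and on universal reaction on placebo; the pooling and the peak-for-onset substitution rest on the SAP rules alone.

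No scores are lost and the medical review can still see the contrast, so this is a correction worth making and not a fatal flaw. It matters because a study with no formal comparison depends on its descriptive summaries, and Protocol section 8 and SAP 4 already call for summaries of this kind.

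**What to change.** Make the change before unblinding, since SAP 4 treats analyses performed after the blind is broken as post hoc.

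1. In the Table 6.1/6.2 shell, replace the first row with two: *No positive reaction (maximal grade below 1 at all visits)* and *Positive reaction, maximum at Day 3*. Restrict the Day 4 to Day 14 rows to subjects with a maximal grade of at least 1. The rows then do not overlap, and subjects with only doubtful scores count as having no positive reaction. Show irritant reactions (no grade) and missing Day 3 scores as separate counts, because nothing is imputed (SAP 8.5).
2. In line with Protocol section 8 and SAP 4, tabulate Day 3 grade and maximal grade by injection type, using the worse of the two sites as Table 6 already does. Add the number of subjects whose rHuPH20 grade is lower than, the same as or higher than their placebo grade. This stays descriptive and delivers the within-subject comparison that SAP 9.1 calls primary.
3. In SAP 9.1, describe the variable as day of peak reaction. For onset, report the first day with grade 1 or above, and state that onset before 48 hours is not observed.

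The cost is some SAP wording and a slightly larger table. All scores are already collected; visits and case report forms do not change.

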9.2 Exploratory Analyses

TEWL (Trans-epidermal water loss) assessments at Baseline (Day 1), Day 3, Day 4 and Day 5 will be summarized for Treatment Regimen 1 and Treatment Regimen 2 by injections type (rHuPH20 or Placebo). Summaries of TEWL assessments will be generated by subject using figures (Figure 2) and listings (Listing 9). A review of the TEWL assessments summaries will be used to investigate possible treatment effect of rHuPH20 or placebo control injection on the exposure to topical nickel allergen.

Analysis of Chromometer readings will be carried in the same manner as the analysis for TEWL assessments (Figure 3, Listing 11). All Chromometers readings reported will be presented in listings; however, only reported “a” scale readings will be considered for figures.

10. SAFETY ANALYSES

All subjects who received study drug will be included in the safety analyses, analyzed according to the study treatment actually received.

10.1 Adverse Events

All adverse event summaries will be restricted to Treatment Emergent Adverse Events (TEAE), which are defined as those AEs that occurred after dosing and those existing AEs that worsened during the study. Verbatim terms on case report forms will be mapped to preferred terms and system organ classes using the MedDRA dictionary (version 12.0).

Each adverse event summary will be displayed for the Safety population. Summaries that are displayed by system organ class and preferred terms will be ordered by descending order of incidence of system organ class and preferred term within each system organ class. Summaries of the following types will be presented:

- Subject incidence of TEAEs and total number of unique TEAEs by MedDRA system organ class and preferred term.
- Subject incidence of TEAEs by MedDRA system organ class, preferred term, and highest severity. At each level of subject summarization a subject is classified according to the highest severity if the subject reported one or more events. A

missing column will be added to the summary table if any TEAEs are reported with missing severity.

- Subject incidence of TEAEs by MedDRA system organ class, preferred term, and closest relationship to study drug (Related/Not Related). At each level of subject summarization a subject is classified according to the closest relationship if the subject reported one or more events. AEs with a missing relationship will be considered related for this summary.
- Subject incidence of serious TEAEs and total number of unique serious TEAEs by MedDRA system organ class and preferred term.
- Subject incidence of TEAEs and total number of unique serious TEAEs leading to discontinuation of study drug or premature withdrawal from study.
- Subject incidence of TEAEs reported after physical examination of injection site and safety review on Day 1 (for Treatment Regimen 2 only), Day 3 through Day 7 and Day 14 will be presented by injection type.

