## 6. STUDY MEDICATIONS AND ADMINISTRATION

### 6.1. Study Medication

rHuPH20 (recombinant hyaluronidase human injection), also designated as Study Drug, will be provided as 12,000 USP units/mL in 1 mL vial. This Study Drug is a concentrated formulation of the FDA-approved rHuPH20 drug product known as HYLENEX (150 USP units/mL), with the exception that Study Drug does not contain calcium chloride and disodium edentate.

Clinical Study Drug placebo will consist of the same formulation of rHuPH20 Clinical Study Drug without active drug substance.

The manufacturing and packaging of the study products will be in accordance with GMP.

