#### **6.4. Randomization and Blinding**

This is a double-blind randomized study. Subjects and the investigative staff will be blinded to the contents of each study drug injection. The pharmacist or designee at the investigative site preparing syringes for injection will not be blinded. The randomization list will be provided by the designated data management team. When a subject is randomized in the study, they must always be assigned to the lowest randomization number (e.g., subject number) available at the time of randomization.

Replacement subjects will be added if a subject discontinues prior to fulfilling the evaluability criteria ([Section 5.2](#)). Replacement subjects must always be assigned to the lowest available subject ID number available from the replacement randomization code.

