#### **7.5. Classification of Adverse Events by Relationship to Study Drug Administration**

The relationship of each AE to the study drug administration will be assessed by the Investigator after careful consideration and according to the following guidelines. Investigators will consider AEs to be either causally related to the therapy or to be not causally related; the following definitions apply:

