**Causally Related:**

The event follows a reasonable temporal sequence from administration of the study drug or in which the drug level has been established in body fluid or tissue; it follows a known or expected pattern of response to the study drug; or it can not be readily explained by well-documented concurrent or co-existent pathological processes, environmental or toxic factors, or other therapy administered to the subject. A causal relationship may be confirmed by improvement following cessation of the study drug or dose reduction, especially if the

reaction reappears following subsequent study drug exposure. The Investigator should refer to the SAE sections in the protocol and to the IB for additional guidance.

If the clinical data are not clear, the Investigator must use his or her best judgment. The AE should be recorded as causally related if the Investigator considers the balance of the available data to be consistent with a study drug effect.

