Subjects Reporting at Least One Adverse Event	n (%)	n (%)	n (%)	n (%)	n (%)
System Organ Class 1	n (%)	n (%)	n (%)	n (%)	n (%)
Preferred Term 1	n (%)	n (%)	n (%)	n (%)	n (%)
Preferred Term 2	n (%)	n (%)	n (%)	n (%)	n (%)
.
System Organ Class 2	n (%)	n (%)	n (%)	n (%)	n (%)
Preferred Term 1	n (%)	n (%)	n (%)	n (%)	n (%)
Preferred Term 2	n (%)	n (%)	n (%)	n (%)	n (%)
.

[1] At each level of summation (overall, system organ class, preferred term), subjects reporting more than one adverse event are counted only once using the highest severity.
path\t_program.sas date time

Table
Treatment Emergent Adverse Events by System Organ Class and Relationship to Study Drug
Safety Population

System Organ Class / Preferred Term [1]	Safety Population (N=)	
	Related	Not Related
Subjects Reporting at Least One Adverse Event	n (%)	n (%)
System Organ Class 1	n (%)	n (%)
Preferred Term 1	n (%)	n (%)
Preferred Term 2	n (%)	n (%)
.		
System Organ Class 2	n (%)	n (%)
Preferred Term 1	n (%)	n (%)
Preferred Term 2	n (%)	n (%)

[1] At each level of summation (overall, system organ class, preferred term), subjects reporting more than one adverse event are counted only once using the closest relationship to study drug.
path\t_program.sas date time

Table 28
Treatment Emergent Serious Adverse Events by System Organ Class
Safety Population

System Organ Class / Preferred Term	Safety Population (N=)	
	Number of Subjects [1]	Number of Events
Subjects Reporting at Least One Serious Adverse Event	n (%)	n
System Organ Class 1	n (%)	n
Preferred Term 1	n (%)	n
Preferred Term 2	n (%)	n
.		
System Organ Class 2	n (%)	n
Preferred Term 1	n (%)	n
Preferred Term 2	n (%)	n

[1] At each level of summation (overall, system organ class, preferred term), subjects reporting more than one serious adverse event are counted only once.
path\t_program.sas date time

Table 29
Treatment Emergent Adverse Events Leading to Discontinuation of Study Drug or Premature Withdrawal of From Study Safety Population

System Organ Class / Preferred Term	Safety Population (N=)	
	Number of Subjects [1]	Number of Events
Subjects Reporting at Least One Serious Adverse Event	n (%)	n
System Organ Class 1	n (%)	n
Preferred Term 1	n (%)	n
Preferred Term 2	n (%)	n
.		
System Organ Class 2	n (%)	n
Preferred Term 1	n (%)	n
Preferred Term 2	n (%)	n

[1] At each level of summation (overall, system organ class, preferred term), subjects reporting more than one adverse event are counted only once.
path\t_program.sas date time

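### No planned table shows whether adverse events judged related to study drug arose at rHuPH20 sites or at placebo sites

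*SAP*

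**What the plan says.** **Rule and table.** SAP 10.1 summarizes treatment-emergent adverse events (TEAEs) by "closest relationship to study drug (Related/Not Related"). At each level, "a subject is classified according to the closest relationship if the subject reported one or more events". It adds that "AEs with a missing relationship will be considered related for this summary". The shell in SAP Appendix B, "Treatment Emergent Adverse Events by System Organ Class and Relationship to Study Drug", has one Related and one Not Related column for the Safety population and no product columns. SAP Appendix A numbers it Table 9.

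**Who judges.** Protocol 7.5: "The relationship of each AE to the study drug administration will be assessed by the Investigator after careful consideration". The first criterion listed for a causal relationship is "The event follows a reasonable temporal sequence from administration of the study drug". Protocol 6.4: "Subjects and the investigative staff will be blinded to the contents of each study drug injection".

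**What study drug means.** Protocol 6.1 opens with "rHuPH20 (recombinant hyaluronidase human injection), also designated as Study Drug". Protocol 6.4, the Regimen 2 text in Protocol 3.1 and 5.3.10, and SAP section 3 use the same term for whatever was randomized to the site, placebo included.

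**Design.** Within each regimen, two sites per subject receive rHuPH20 and two receive placebo (Protocol 3.1 and 5.3.10). Every injection site reaction must be recorded as an adverse event, whichever product was given (Protocol 5.3.17).

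**What is split by product.** SAP 10.1 (last bullet) and Table 12 show TEAEs from the site examinations and safety reviews by regimen and injection type, without relationship. Protocol section 8 says that collected data, safety included, will be summarized by treatment group. It also lists relatedness among the adverse-event tabulations.

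**The concern.** Safety and tolerability of the rHuPH20 injection is a primary objective in both documents. A table headed by relationship to study drug, in a protocol that designates rHuPH20 as Study Drug, invites reading its Related column as an rHuPH20 rate. The column is the rate of subjects with at least one event, at any of eight sites or elsewhere, that a blinded Investigator attributed to an injection or for which the relationship was left blank.

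The SAP's statement that safety is analysed by treatment actually received does not separate the products, because every fully dosed subject receives both. The relatedness data therefore cannot show whether related events cluster at rHuPH20 sites. The within-subject placebo control, which could answer that, is not used for this variable.

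**Working it through.** **1. Inputs from the documents.** Sites per subject: 4 rHuPH20 + 4 placebo = 8. Injections: Regimen 1, 4 × 5 = 20; Regimen 2, 4 × (1 + 5) = 24; total 44, of which 22 are placebo. Check: 22 × 3,000 U = 66,000 U of rHuPH20 per subject, below the 96,000 U that Protocol 1.3 says exceeds the expected cumulative dose. The count fits the protocol.

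**2. Inputs not in the documents.** Neither document gives a site-reaction rate or a share of reactions judged related, so there is no planned figure to reproduce. Let p be the chance that a site yields at least one event judged related (or left blank) over the course. Assume p is equal for both products, which means no drug effect. Let ρ be the correlation between sites within a subject. Both are assumptions, shown over a range.

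**3. Formulas.**
- Independent sites: P(any of n sites) = 1 − (1 − p)^n, with n = 8 for the pooled column and n = 4 for one product.
- Correlated sites (beta-binomial): a = p(1 − ρ)/ρ, b = (1 − p)(1 − ρ)/ρ, and P(any of n) = 1 − Γ(b+n)Γ(a+b) / [Γ(b)Γ(a+b+n)].
- Share of Related subjects with placebo-site events only: [P(any of 8) − P(any of 4)] / P(any of 8).

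**4. Results with no drug effect.**

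| p per site | ρ | Pooled Related (8 sites) | Each product (4 sites) | Placebo-only share of Related |
|---|---|---|---|---|
| 5% | 0 | 33.7% | 18.5% | 45% |
| 5% | 0.2 | 21.4% | 14.4% | 33% |
| 5% | 0.5 | 12.9% | 10.1% | 22% |
| 10% | 0 | 57.0% | 34.4% | 40% |
| 10% | 0.2 | 38.8% | 27.1% | 30% |
| 10% | 0.5 | 24.4% | 19.4% | 20% |
| 20% | 0 | 83.2% | 59.0% | 29% |
| 20% | 0.2 | 63.9% | 48.4% | 24% |
| 20% | 0.5 | 43.9% | 36.2% | 18% |

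Worked line, p = 10%, independent: 1 − 0.9^8 = 0.570; 1 − 0.9^4 = 0.344; (0.570 − 0.344)/0.570 = 0.40.

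**5. Where the pooled share reaches half.** With independent sites, p = 1 − 0.5^(1/8) = 8.3%. With ρ = 0.2 the crossing lies between p = 10% and 20%. With ρ = 0.5 it lies between 20% (43.9%) and 30% (59.2%).

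**6. Effect of the causality judgment.** If a site reacts with probability 20% and half of reactions are judged related, p = 0.20 × 0.5 = 10% and the pooled share is 57.0% rather than 83.2% (independent sites).

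**7. With the split.** The two product columns have equal expectation when there is no drug effect (34.4% each at p = 10%, independent), so the expected difference is zero. The pooled column has no comparator.

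**The case against.** - **The SAP already compares site events by product.** A reader might infer that it does not, but Table 12 gives subjects and events for rHuPH20 and placebo within each regimen. If every site reaction were at a placebo site, Table 12 would show it. This stands and narrows the gap to relationship by product. Table 12 covers only events from the site examinations and safety reviews, and its first row is labelled as serious events although the title covers all TEAEs.
- **Related is a judgment.** A reader might infer that every placebo-site reaction is recorded as related. Protocol 7.5 asks for the balance of the data and allows Not Causally Related. Each site also carries a nickel patch, an obvious alternative cause. A placebo-site reaction can count; it need not.
- **Blinded causality cannot use product.** True, and it is not a fault. Only the later tabulation is open to criticism.
- **The term is used both ways.** Much of the text uses study drug for either product, and the pooled column fits that use. This makes it a labelling problem rather than a miscalculated table, but Protocol 6.1 still points the other way.
- **Nothing is triggered.** No formal comparison is planned and no stopping rule uses this table. That limits the consequence to interpretation.
- **Site is an imperfect proxy for product.** Protocol 1.1 describes hyaluronidase as increasing dispersion, and the visible text gives no spacing between sites. This stands as a caveat on any split by site.

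**Conclusion.** The relationship table pools four rHuPH20 and four placebo sites per subject. No planned table shows whether related events come from rHuPH20 sites, although Protocol section 8 promises safety data by treatment group. This rests on the text alone and needs no assumed rate.

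The size does rest on assumptions. At p = 10% per site with no drug effect, the pooled Related share is 57%, 39% or 24% at ρ = 0, 0.2 or 0.5. About 40%, 30% or 20% of those subjects reacted only at placebo sites.

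A reader might infer that most subjects will be classed as related without any drug effect. The documents do not support that: it needs p above 8.3% with independent sites and a higher p with clustering, and no rate is given. Nor do they support restricting related to rHuPH20 to events at rHuPH20 sites. Every fully dosed subject received rHuPH20, so a systemic event judged related remains possible rHuPH20 harm.

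This is a low-cost improvement to the reporting, not a flaw that invalidates the safety analysis.

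**What to change.** 1. For site-localized TEAEs, present Related/Not Related by injection type. Either add relationship to Table 12 or split the relationship table by the product given at the site, using the per-site adverse-event numbers in Listings 14 and 15. Confirm that the adverse-event dataset carries the same number, because the Listing 16 shell does not display it. State how an event record covering sites of both products is counted.
2. Show missing relationship as its own count by product, beside the rule that treats it as related.
3. Keep non-site events judged related in the related count, under a separate heading such as *related, not assignable to one product*. Do not remove them from possible rHuPH20 harm.
4. Retitle the pooled column *related to study injection (rHuPH20 or placebo)* and use one definition of study drug in both documents.
5. Correct the first-row label of Table 12.

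Cost: SAP wording, an aligned definition in the protocol, and one column split in an existing table. No new data are needed and the blind is unaffected, since the split is made at analysis.
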